1.4.2 Secondary objectives

- 1. Assess mortality on days 7, 14 and 28 after hospitalization;
- 2. Evaluate indicators of clinical worsening (use of supplemental oxygen, ICU stay, length of stay in the ICU, length of hospital stay, need for intubation and time on mechanical ventilation, radiological alterations and time to improve the radiological and resonance pattern);
- 3. Assess the percentage of SARS-CoV2 detection in oropharyngeal swab, nasal and blood swab samples on days 1, 3, 5, 8, 11, 14 and 28, in the study population;

- 4. Quantify the virus that causes SARS-CoV2 in oropharyngeal swab, nasal and blood swab samples on days 1, 3, 5, 8, 11, 14 and 28, in the study population;
- 5. Cumulative incidence of adverse events (AEs);
- 6. Cumulative incidence of grade 3 and 4 serious adverse events (SAEs);
- 7. Discontinuation or temporary suspension of treatment (for any reason);
- 8. Alterations in white cell count, hemoglobin, platelets, creatinine, glucose, total bilirubin, ALT and AST over time;
- 9. In case of mortality, describe organic alterations via autopsy.

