1.4.2 Secondary outcomes

- 1. Mortality on days 7 and 14;
- 2. Clinical status of the study subject on days 14 and 28;
- 3. Daily clinical status during hospitalization;
- 4. Time on supplemental oxygen (if applicable);
- 5. Time on mechanical ventilation (if applicable);
- 6. Length of hospitalization;
- 7. Data and cause of death (if applicable);
- 8. Incidence of adverse events;

9. Incidence of serious adverse events (grades 3 and 4).

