1.11.1 Follow-up duration

An individual will complete the study in 28 days, starting from their inclusion.

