- # Participant may be hospitalized or discharged. In the latter case, there will be no outpatient return visit and the main outcome will be assessed by telephone. Note: all procedures will be performed during the hospitalization period and will be interrupted if the participant is discharged;
- a Inclusion/exclusion criteria will be fully assessed at visit D1, prior to inclusion. The diagnosis of SARS-CoV2 will occur a posteriori.
- b Randomization will take place in blocks of 4 with 110 participants each. There will be interim reviews when 25%, 50% and 75% of participants are included;
- c A complete medical history will be obtained prior to randomization to include assessments of cardiovascular, metabolic (for example, Type I or II diabetes mellitus), psychiatric (such as depression), renal (such as nephrolithiasis, nephropathy, renal failure) and bone disorders;
- d Physical examination will consist of evaluation of vital signs (heart rate, respiratory rate, systolic, diastolic and mean blood pressure, peripheral oxygen saturation) and signs and symptoms present;
- e Assessments to highlight any visual and/or mental alterations resulting from chloroquine;
- f Avoid administration of other drugs known to prolong the QT interval (ie quinolones, macrolides, ondansetron), as well as various antiarrhythmic, antidepressant and antipsychotic drugs; Avoid administration of other drugs known to prolong the QT interval (ie quinolones, macrolides, ondansetron), as well as various antiarrhythmic, antidepressant and antipsychotic drugs;
- g A 12-lead ECG will be performed in a semi-supine position after resting for at least 5 minutes. The intention is to exclude the development of prolongation in the QT interval or bradycardia;
- h Blood samples will be collected to assess the COVID-19 infection and perform laboratory tests requested by the doctor. In the case of Manaus, the evaluation of the infection by COVID-19 will take place at LACEN-FVS and the others will take place at the Delphina Rinaldi Abdel Aziz Hospital and A & E. In Niterói-RJ all tests will be performed at the hospital. In Mato Grosso do Sul, the evaluation of infection by COVID-19 will take place at LACEN-MS and any others will take place at participating hospitals;

Version 2.0 23march2020

- i Blood samples will be collected for storage in a biorepository for further evaluation of the immune response profile;
- j Evaluated according to the DAIDS table for clinical and laboratory events;

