3. OBJECTIVES AND OUTCOMES

The general objective of the study is to evaluate the clinical efficacy, safety of therapy and reduction of mortality in hospitalized adult patients with severe respiratory syndrome using two different dosages of chloroquine. Objectives and outcomes are shown in table 2.

 Table 2: Objectives and outcomes.

| Objectives | Outcomes | | | | | | |
|--|---|--|--|--|--|--|--|
| Primary | | | | | | | |
| To assess whether the therapeutic regimen of | Reduction of mortality by 50% | | | | | | |
| Group 1 reduces mortality by 50% in the study | | | | | | | |
| population compared to Group 2. | | | | | | | |
| Secondary | | | | | | | |
| - Assess mortality on days 7, 14 and 28 after | - Mortality on days 7 and 14 | | | | | | |
| hospitalization; | - Clinical status of the subject on days 14 | | | | | | |
| - Assess clinical improvement (use of | and 28 | | | | | | |
| supplemental oxygen, ICU stay, length of stay | -Daily clinical status during | | | | | | |
| in the ICU, length of hospital stay, need for OTI | hospitalization | | | | | | |
| and time on mechanical ventilation, radiological | - Need for and duration of supplementary | | | | | | |
| alterations and time taken to improve the | oxygen | | | | | | |
| radiological and resonance pattern); | - Need for and duration of mechanical | | | | | | |
| - Assess the percentage of SARS-CoV2 | ventilation | | | | | | |
| detection in OPS and blood samples on days 1, | - Length of hospitalization | | | | | | |
| 3, 5, 7, 14 and 28 in the study population; | - Data and cause of death (if applicable) | | | | | | |
| Quantify the SARS-CoV2 virus in | - Prevalence of grade 3 and 4 adverse | | | | | | |
| oropharyngeal swab, nasal swab, OPS and blood | events; | | | | | | |
| samples on days 1, 3, 5, 7, 14 and 28 in the study | - Prevalence of serious adverse events; | | | | | | |
| population; | - Leukogram, hemoglobin, platelets, | | | | | | |
| - Alterations in white cell count, hemoglobin, | creatinine, CK, glucose, total bilirubin, | | | | | | |
| platelets, creatinine, glucose, total bilirubin, | ALT and AST on days 1, 3, 5, 7 (while | | | | | | |
| ALT and AST over time. | hospitalized); and on days 14 and 28 (if | | | | | | |
| - Cumulative incidence of serious adverse | patient is able to return to the clinic or is | | | | | | |
| events (SAEs); | still hospitalized); | | | | | | |
| - Cumulative incidence of grade 3 and 4 adverse | - Negative presence of the virus in | | | | | | |

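### Adverse-event and SAE recording is written to end at discharge, so the observation window is the length of stay, although follow-up is 28 days and study drug runs to day 10

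*Protocol*

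**What the plan says.** The protocol describes the safety window in several places.

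- **Table 1 (section 1.12)** marks adverse-event recording in every column from D0 to D28. The D14 and D28 column heads carry footnote #. That footnote rules out an outpatient return visit, leaves the main outcome to a telephone call, and adds that "all procedures will be performed during the hospitalization period and will be interrupted if the participant is discharged".
- **Section 5.5.2** says follow-up takes place within the hospital stay.
- **Section 1.11.1** says: "An individual will complete the study in 28 days, starting from their inclusion".
- **Section 8.1.1** keeps study drug going for 10 days irrespective of hospitalisation and has patients discharged earlier contacted on the evaluation days. It does not say what is asked.
- **Table 2 (section 3)** foresees day-14 and day-28 laboratory results if the patient can come back to the clinic.

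The name of the measure also varies. The objectives column of Table 2 has "Cumulative incidence of grade 3 and 4 adverse" events. The outcomes column of the same table has "Prevalence of grade 3 and 4 adverse" events and "Prevalence of serious adverse events". The secondary outcomes in section 1.5 have "Incidence of adverse events".

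**The concern.** Comparing the safety of two chloroquine doses is part of the general objective in section 3. If recording stops at discharge, a patient who leaves on day 7 is observed for 7 days and one who stays is observed for up to 28. Length of hospitalisation is a secondary outcome in section 1.5 and may depend on dose. A crude proportion with an event then mixes toxicity with time under observation, and the arm that goes home sooner looks safer at the same true rate. Early death shortens the window as well.

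The loss may also fall on treatment days. Under section 8.1.1 a patient discharged before day 10 may still be on study drug. By the dosing table in section 6.2, on days 6 to 10 Group 1 takes chloroquine and Group 2 takes only placebo. Section 6.1 gives a plasma half-life of 72 to 120 hours and a terminal half-life of 30 to 60 days, so exposure outlasts discharge.

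**Working it through.** **1. Reading the text.** Footnote # and section 5.5.2 agree with each other: observation ends at discharge, apart from the main outcome. Three places do not fit with that: 28 days per participant (1.11.1), study drug and contacts that can continue after discharge (8.1.1), and the clinic return (Table 2), which footnote # excludes. Section 9.2 adds that laboratory abnormalities of grade 2 or more are monitored until they resolve or stabilise, which cannot be met if procedures end at discharge. No section sets a time at risk for adverse events.

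**2. The plan's own figure.** The protocol states no adverse-event rate and no expected stay, so there is none to reproduce here. The number per arm comes from the mortality calculation in section 5.1: (1.96 + 0.842)² × (0.2×0.8 + 0.1×0.9) / 0.1² = 196.2, hence 197 per group and 394 in total. Allowing for 10% losses, 394 / 0.9 = 438, close to the stated 440. I use 220 per arm.

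**3. Consequence under stated assumptions.** Assume a constant event hazard h per day, equal in both arms, and recording that stops on day t. The proportion recorded is 1 − exp(−h·t). The chance of a two-sided p<0.05 in favour of the shorter-stay arm is approximately Φ(d/SE − 1.96), where d is the difference in recorded proportions and SE = √[p₁(1−p₁)/220 + p₂(1−p₂)/220]. The opposite tail adds less than one percentage point in the rows below.

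| Assumed h | Recorded, 14 days | Recorded, 10 days | d / SE | Spurious p<0.05 |
|---|---|---|---|---|
| 0.5%/day | 6.8% | 4.9% | 0.0188 / 0.0223 = 0.84 | 13% |
| 1%/day | 13.1% | 9.5% | 0.0355 / 0.0301 = 1.18 | 22% |
| 3%/day | 34.3% | 25.9% | 0.0838 / 0.0436 = 1.92 | 49% |

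**4. Sensitivity to the assumptions.**
- Equal stays: the two proportions are identical and the error rate stays at 5%.
- 12 against 11 days at 3% per day: 30.2% against 28.1%, and about 7%.
- Stays exponentially distributed with means m of 14 and 10 days, at 3% per day, ignoring the day-28 limit: the recorded proportion is h·m/(1 + h·m), that is 0.42/1.42 = 29.6% and 0.30/1.30 = 23.1%. The chance falls from 49% to about 34%.
- All events in days 1 to 10, and both stays at least 10 days: no bias. With stays of 7 and 14 days and a true risk of 20%, the recorded proportions are 1 − 0.8^0.7 = 14.5% and 20%, a ratio of 0.72.
- A common window to day 28: both arms show the same proportion, for example 1 − exp(−0.03×28) = 57% at 3% per day.

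**The case against.** The strongest reply is that the text is unclear about events after discharge but does not exclude them. Section 8.1.1 has early-discharged patients contacted on evaluation days, and every evaluation day in Table 1 carries the adverse-event row. Section 9.1 allows data from interviews with patients or caregivers. Section 9.5 requires all events to be reported, and section 9.6 makes hospitalisation a seriousness criterion. A reader might infer that serious events after discharge will simply not be counted; the documents do not support that. What stands is that no section says the contacts collect events, while footnote # names only the main outcome.

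Three other stronger readings also fail.

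- *Table 1 contradicts its own footnote.* Footnote # is attached to D14 and D28 and can properly limit those marks. The firmer conflict is with sections 1.11.1 and 8.1.1 and with Table 2.
- *The word prevalence would count conditions present at entry and so drives the bias.* Section 9.5 already limits recorded symptoms to those that occur or worsen during the study. The label is a separate inconsistency and does not cause the bias.
- *The plan tests adverse-event proportions by chi-square with no regard to time.* Section 10.1 assigns chi-square and Fisher tests to qualitative variables in general. The adverse-event analysis may be set out in a statistical analysis plan that is not at hand. An analysis plan could allow for time at risk, but it could not recover events that were never recorded.

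The on-drug gap also depends on section 8.1.1 meaning that dosing goes on after discharge. Section 6.8 has a study pharmacist give each dose and observe the patient for 30 minutes, and the protocol does not say how this works after discharge. These two sections need to be reconciled.

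**Conclusion.** The point holds in conditional form. As written, AE and SAE capture depends on length of stay, and events after discharge, possibly including some on study drug, can be missed. A between-arm bias needs two further conditions: stays that differ by arm, and events that continue after discharge. Its size cannot be taken from the documents. The 13% to 49% range rests on an assumed constant hazard of 0.5% to 3% per day and a 4-day difference in observation that is the same for every patient in an arm. A reader might take the upper figure as the expected false-positive rate. The documents do not support that, because they give neither event rates nor stays, and with equal stays there is no excess. Even then, events after discharge could still be lost in both arms.

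Day-28 mortality is not affected, since it is taken by telephone after discharge. The point concerns secondary safety outcomes and should be corrected because the comparison of doses relies on them. The incidence/prevalence wording is a smaller, separate correction.

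**What to change.** 1. In footnote # of Table 1 and in section 8.1.1, state that the contacts after discharge (evaluation days up to day 10, D14 and D28) also ask about serious adverse events and readmission.
2. Define the SAE outcome as the proportion of randomised patients with at least one SAE from first dose to day 28, the same window in both arms.
3. Define non-serious adverse events, including non-serious grade 3 and 4 events, as an in-hospital measure reported per patient-day at risk. A day-28 proportion for all adverse events is not obtainable if the calls ask only about SAEs and readmission, so the two measures should be kept apart.
4. Replace prevalence with cumulative incidence in the outcomes column of Table 2 and align section 1.5, in keeping with section 1.4.2 and with the occur-or-worsen rule in section 9.5.
5. Reconcile section 1.11.1, Table 1 and footnote #, section 5.5.2, section 8.1.1 and the clinic-return wording in Table 2.

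The cost is wording and two questions in contacts that are already planned. Events reported by telephone are less detailed than ward records, so some dependence on stay remains. If events cluster early, a rate per patient-day is diluted by a longer stay, so time at risk should be shown beside it.

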1.5 Study outcomes

1.4.1 Primary outcome

- 50% mortality reduction by day 28.

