1.11 Study duration

The study will last for the period of appearance of cases (expected between April 6th and August 31st, 2020), or until the sample is completed, or until the interim analysis shows a clear benefit or harm. The period was calculated based on our modeling of the number of cases in Manaus, as shown below.

To obtain a possible scenario of infected by COVID-19 in the city of Manaus, we used simulation using the SIR model (Susceptible, Infected and Recovered) to have an idea of the probable period when we will have the peak of infection in the city of Manaus. The parameters used for the modeling were as follows: R0 = 2.5, from studies in China; the Susceptible rate 0.92, the infected rate 0.01 and the Recovered rate 1/14. The first case found in Manaus was diagnosed on March 11^{th} , 2020.

The obtained result can be seen in the graph below.

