10.2 Sample calculation and interim analysis

The sample for the primary outcome (reduction in lethality in patients with severe respiratory virus treated with a high dosage of chloroquine compared to a low dosage) was calculated based on the following assumptions:

- 3. The 20% lethality incidence in critically ill patients per year in the low dosage group;
- 4. High dosage chloroquine will be able to reduce lethality by at least 50% compared to low dosage chloroquine;

Thus, considering a test of differences in proportions between 2 groups of the same size, with power of 80% and alpha of 5%, 394 participants will be needed (197 per group). Considering 10% losses, the sample size is 440 participants.

To include interim analyses, we recalculate the sample sizes required in each of the analyzes and in the final analysis, using an alpha-spending function approach, in which the type 1 error is controlled by alpha correction final, based on the alphas used for interim analyses. There are several alpha spending functions and there is always a trade-off between how much will be 'spent' on the interim analysis and the final sample size required. In summary, the more difficult it is to reject the null hypothesis in the interim analysis, the less alpha will be spent and the impact will not be large. We will use Hwang-Shih-DeCani spending functions with $\gamma = -4$ for the upper limit (that is, to interrupt the study that rejects the null hypothesis in the interim analysis), which corresponds to a conservative method, equivalent to the upper limit of O 'Brien-Fleming, with little impact on the final sample size. We will also include a lower limit for testing futility, also using the Hwang-Shih-DeCani spending function, but with a less stringent $\gamma = -2$ parameter for a beta spending function. Although the calculation includes a possible interruption due to futility, this can be ignored, at the discretion of the DSMB (or equivalent) without any impact on the type 1 error.

The table below shows the calculations for the 3 interim analyses and for the final analysis, showing both the sample size required in each analysis as well as the upper (one-tailed 2.5%) and lower limits.

| | | | Superior Limit | | | |
|------------|---|----|----------------|--------|-----|--------------|
| Sample | | | | | | |
| size | | | | p one- | | |
| percentage | | N | Z | tailed | Z | p one-tailed |
| | | 10 | - | 0.278 | 3.1 | |
| 25% | 8 | | 0.59 7 | 6 | | 0.0008 |

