| | | 21 | 0.3 | 0.638 | 2.8 | |
| 50% | 5 | 5 | 6 | 2 | | 0.0024 |
| | | 32 | 1.1 | 0.882 | 2.4 | |
| 75% | 2 | 9 | 1 | 4 | | 0.0074 |
| | | 42 | 2.0 | 0.978 | 2.0 | |
| 100% | 9 | 1 | 0 | 1 | | 0.0220 |

The procedure will be based on the calculation of the Z value of the difference of proportions test in each of the analyses, and the study will continue if this value is between the values of the lower and upper limits and will be interrupted if it is above the upper limit (by rejection H0) or below the lower limit (for futility), remembering that the latter can be ignored without prejudice to the calculations.

All calculations in this report were made in the R environment, version 3.6.1, with the functions implemented in the TrialSize and gsDesign packages. Other intermediary analyzes can be carried out throughout the study to periodically monitor the safety of participants and will provide possible prior information on treatment to the DSMB and Ministry of Health.

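### Interim looks are triggered on inclusion, but the Z limits in section 10.2 hold only at 25/50/75% of the day-28 information, and the protocol does not reconcile the two

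*Protocol*

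**What the plan says.** - **Timing.** Protocol section 1.12, Table 1, footnote b: "There will be interim reviews when 25%, 50% and 75% of participants are included". With 440 participants, that is at 110, 220 and 330 included.
- **Endpoint.** Section 1.5 defines the primary outcome as "50% mortality reduction by day 28". Section 1.11.1 adds: "An individual will complete the study in 28 days, starting from their inclusion".
- **Statistic and rule.** Section 10.2: "The procedure will be based on the calculation of the Z value of the difference of proportions test in each of the analyses". The trial continues while Z lies between the tabulated limits. It stops above the upper limit for efficacy and below the lower limit for futility. Section 10.2 says twice that the futility limit may be ignored without affecting type 1 error, and leaves this to the DSMB.
- **Limits.** They come from Hwang-Shih-DeCani spending, with gamma -4 for the upper limit and gamma -2 (beta spending) for the lower. They are tabulated at 25/50/75/100%, with sample sizes 108/215/322/429.
- **Accrual window.** Section 1.11: "expected between April 6th and August 31st, 2020".

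The protocol does not say how participants short of day 28 are counted at a look, or that the limits will be recomputed at the information actually available.

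**The concern.** A group-sequential limit belongs to an information fraction. With a binary day-28 outcome, information is the number of participants whose day-28 status is known, not the number included. An inclusion trigger ensures that the last 28 days of recruits have not completed follow-up when Z is calculated.

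If they are left out, Z rests on fewer patients than the limit was built for. A lower limit set for 25% information is then too easy to cross by chance. If they are counted by deaths so far, survivors who may still die count as successes, and Z is no longer the day-28 comparison that the design was based on.

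At stake is a recommendation to stop for futility while the planned effect is real, based at the first look on very few evaluable patients.

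**Working it through.** **1. Reproduce the plan's figures.** The inputs are in section 10.2: "The 20% lethality incidence in critically ill patients per year in the low dosage group"; "High dosage chloroquine will be able to reduce lethality by at least 50% compared to low dosage chloroquine"; "with power of 80% and alpha of 5%, 394 participants will be needed (197 per group".

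Fixed design, unpooled variance: n per arm = (1.960 + 0.842)² × (0.2×0.8 + 0.1×0.9) / 0.1² = 7.849 × 0.25 / 0.01 = 196.2, so 197 per arm and 394 in total. This matches.

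Sequential design, with one-sided alpha 0.025, beta 0.20 and t = 0.25/0.50/0.75/1:
- Alpha spent = 0.025(e^{4t} - 1)/(e^4 - 1) = 0.0008/0.0030/0.0089/0.0250.
- Beta spent = 0.20(e^{2t} - 1)/(e^2 - 1) = 0.020/0.054/0.109/0.200.
- Numerical integration gives upper Z 3.16/2.82/2.44/2.01 (one-tailed p 0.0008/0.0024/0.0074/0.0220) and lower Z -0.59/0.35/1.19/2.01 (p 0.279/0.639/0.882/0.978).
- Inflation is 1.0873, and 394 × 1.0873 = 428.4, so 429.

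These agree with the protocol's table, read through its one-tailed p-values because the table is broken in the text. The limits therefore assume 25/50/75/100% of the day-28 information. The drift at full information is 2.802 × √1.0873 = 2.921.

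**2. Information present at an inclusion trigger.** 6 April to 31 August is 147 days. Uniform accrual is an assumption: 440/147 = 2.99 per day, so 28 × 2.99 ≈ 84 participants are short of day 28 at any look.
- Completers: 110 - 84 = 26; 220 - 84 = 136; 330 - 84 = 246.
- Information (divided by 429): 0.061/0.317/0.573.

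**3. First look by hand, under 20% vs 10%.** P(futility) = Φ(-0.587 - 2.921√t).
- Planned, t = 0.25: Φ(-2.05) = 0.020.
- Inclusion trigger, t = 0.061: Φ(-1.31) = 0.095.

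**4. All looks, tabulated limits held fixed, completers only, futility followed.**

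| | Cumulative false futility, looks 1/2/3 | Power |
|---|---|---|
| As planned | 2.0 / 5.4 / 10.9% | 80% |
| Inclusion trigger, 147 days | 9.5 / 16.6 / 24.3% | 69% |

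With 440 as the denominator, the total is 25.0%. A patient-level simulation (20,000 trials, blocks of 4) gives 25.7% against 11.0% with complete follow-up.

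**5. Sensitivity (the ranges cover denominators 429 and 440).**

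| Accrual of 440 over | Completers at looks 1/2/3 | False futility by look 3 | Power |
|---|---|---|---|
| 90 days | 0/83/193 | 29-30% | 65% |
| 120 days | 7/117/227 | 33-34% | 61-62% |
| 147 days | 26/136/246 | 24-25% | 69% |
| 170 days | 37/147/257 | 21-22% | 72% |
| 200 days | 48/158/268 | 19% | 74% |
| 250 days | 61/171/281 | 16-17% | 76% |

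At 90 days the first look has no completers and is skipped. At 120 days the normal approximation is rough for the first look.

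- **Deaths to date among all included.** Simulation with assumed exponential times to death (median 5-14 days, truncated at day 28) and accrual over 119-147 days gives false futility of 12.6-15.9% and power of 77-79%.
- **Futility ignored.** At 147 days, one-sided alpha is about 0.027 instead of 0.025, and power is about 83%.

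**The case against.** The strongest reply has four parts.

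- **Section 10.2 can be read as already requiring evaluable participants.** It speaks of the sample size required in each analysis, so footnote b may be shorthand. Footnote b is loosely worded elsewhere too: its description of the randomisation blocks does not match section 7. Data cut-offs are often left to an SAP or DSMB charter. This has some force. But the protocol itself fixes the trigger, the statistic, the limits and the stopping rule, and as written they do not fit together.
- **The futility limit is non-binding.** A DSMB shown 26 completers need not stop. This stands, and it makes the loss of power a risk and not a certainty. It does not repair a miscalibrated limit, because the default rule is still to stop below it.
- **Accrual is not stated.** The window in section 1.11 comes from an epidemic curve with a peak, and recruitment may also end when the sample is complete. The multiplier falls below two once accrual takes longer than about 165-170 days.
- **Completers-only analysis is not stated.** Counting deaths to date gives 1.15 to 1.45 times the planned rate.

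A reader might infer that false futility stops will more than double. The documents do not support that as a fact. It needs a completers-only Z, accrual within about 165-170 days, and a futility limit that is followed. The protocol specifies neither the first nor an accrual rate, and it makes the third optional.

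**Conclusion.** The mismatch holds as the protocol is written: the trigger counts inclusions, the limits require day-28 information, and nothing connects them.

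Its size is conditional. With completers only, roughly uniform accrual over 147 days and the futility limit followed, false futility stops under 20% vs 10% can rise from about 11% to 24-25%, and power can fall from 80% to about 69%. The rise is smaller with slower accrual or with deaths to date, and larger if accrual is somewhat faster. If futility is ignored, only a slight inflation of alpha remains.

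Confidence is high on the mismatch and moderate on the magnitude. It should be fixed before the first formal look, but it does not by itself invalidate the design.

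**What to change.** State the same rule in footnote b and section 10.2:

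- **Who enters Z.** Participants who have reached day 28, taken in randomisation order. Selecting everyone with a known outcome would be wrong, because a recent recruit who has died is known while a recent survivor is not, so deaths would be over-represented.
- **Which limits apply.** Recompute both limits at each look from the stated Hwang-Shih-DeCani functions at t = completers/429. In the 147-day case, cumulative beta spent becomes 0.4/2.8/6.7%. The lower limit at the first look moves from -0.59 to about -1.93: the normal quantile for 0.0041 is -2.65, plus 2.921 × √0.061 = 0.72.

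This keeps the calendar timing and costs a few sentences and a routine calculation at each look.

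The alternative is to keep the tabulated limits and hold each look until the first 108/215/322 randomised have reached day 28. That delays the formal looks by about four weeks. At about 3 per day, some 108 + 84 = 192, 215 + 84 = 299 and 322 + 84 = 406 of 440 would already be enrolled, so the third look could spare only about 34 participants. Recomputing is therefore preferable.

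The safety reviews in sections 1.11.2, 7 and 10.2 are separate and keep their timing under either option.
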